#### *2.3.4 Female Sexual Function Index (FSFI; Rosen et al., 2000)*

The FSFI is a 19-item questionnaire that measures six domains: desire, arousal, lubrication, orgasm, satisfaction and pain. The questionnaire has been used in different clinical trials and epidemiological studies and have shown to have high test-rested reliability and validity, it is scored from 1 to 5 with different response options. The FSFI is completed upon recruitment and at the 1 month follow up.

#### *2.3.5 State Self Compassion Questionnaire (SSCS-S; Neff et al., 2021)*

The SSCS-S is a 6-item questionnaire scored on a 5-point scale from 1 (not very true for me) to 5 (very true for me). In one study, Neff et al (2021) reports the SSCS-S had a strong correlation ( $r=.96$ ) to the long version of the state self-compassion questionnaire and showed good reliability ( $\alpha = .86$ ). Another study found strong construct validity. The SCSS-S is completed upon recruitment and at the 1 month follow up.

#### *2.3.6 Client Satisfaction Questionnaire (CSQ; Larsen et al., 1979)*

The CSQ is an 8-item questionnaire scored on a 4-point scale and will be provided to participants at follow up to ask the acceptability and satisfaction towards the intervention. The questionnaire has high construct validity and internal consistency. Permission has been seeked to adapt the questionnaire to focus on satisfaction for the intervention instead of service satisfaction. Awaiting response. The questionnaire is only used at follow up.

[figure not shown]
#### *2.3.7 Feedback Form*

A short qualitative feedback form will be provided to participants. This form has been developed with experts by experience and will have open ended questions for participants to provide more detailed feedback about the intervention. The questionnaire is only used at follow up.

#### **2.4 Expert by experience (EbE) involvement**

Survivors of sexual assault were consulted during the development of this study to provide feedback on the session materials and measures used throughout the study. EbE's helped develop the visual analogue scales as well as provide feedback on the intervention scripts and handouts which were implemented in the final version.

### 3. Study procedure

*Figure 1. Flow chart of study procedures*

The study is conducted via Qualtrics, an online survey platform. A survey link will be emailed to participants for them to complete in their own environment. This allows the study to be completed anywhere. The survey will be live for 5 months of data collection before being taken offline. Participants will also be sent handouts of each week's intervention. After completing the screening questionnaire, eligible participants will be asked to fill in the FSDS-R, FSFI and SCSS. These questionnaires are filled in once weekly during phase A and B.

During Phase A which varies between 5- 14 days, participants will be sent Qualtrics links to where fill in visual analogue scales daily. The number of days' participants will be in baseline will be randomly allocated. There are 6 visual analogue scales that measure shame, guilt, self-criticism, self-compassion, normalising and motivation.

During phase B participants go through 1 module of the guided-self-help materials each week and complete the same visual analogue scales from baseline every day. After phase B. participants will be invited for a follow-up appointment one month after the intervention to fill in the FSDS, FSFI, SSCS-S client satisfaction questionnaire and feedback form developed with experts by experience.

### **3.1 Informed consent procedures**

Participants will be asked for informed consent via the Qualtrics survey which states they are aware of the consequence of taking part in the study and understand the information sheet provided to them. Participants are also provided with the email address of the Chief Investigator who they can reach out to with any queries before or after taking part. The study advertisement will provide brief information about the study. If interested, women will be directed to the online weblink to read through more detailed study information. It will be clearly stated that participation is voluntary and participants may drop out at any time and withdraw consent even after completing the project. It will be clearly stated that the intervention is

provided through online self-help that individuals work through on their own and does not entail personal support from a psychology team. Through a weblink, participant will tick boxes to provide informed consent, confirming they consent and understand these terms and asked to write their name as a way of providing consent.

### **3.2 Data collection methods**

Data collection will be conducted through Qualtrics. During phase A and B, data is collected daily.

### **3.3 Statistical analysis of data**

Descriptive statistics will be completed for demographic information. Visual analysis will be performed for daily VAS ratings to evaluate the reliability of treatment effects between the baseline and treatment phases. To investigate if there is pre-and post-difference between scores a reliable change index (RCI) will be calculated for each measure using Jacobson & Traux (1991) to test if changes are statistically significant. Tau-U test will be used on outcomes to analyse non-overlap of intervention scores. Guidance and procedures will be followed from What Works Clearing House (Kratochwill et al., 2010).

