## **2. Methods**

### **2.1 Study design**

The study adopts a single-case experimental design (SCED). This study design is helpful in testing the novelty and feasibility of an intervention.

Potential participants will be invited to follow a link to a Qualtrics survey. The Qualtrics survey provides detailed information about the study. Participants will undergo screening for eligibility and risk via Qualtrics. Should individuals wish to participate and are eligible, they can give informed consent by reading a set of statements on Qualtrics relating to the study

information. Eligible participants will fill in questionnaires such as the FSDI, FSFI, SCSS-S, at this point. Participants will undergo a baseline period known as phase A, varying between 5- 14 days where they will fill in visual analogue scales daily. The number of days participants will be in baseline will be randomly allocated by a randomiser. There are 6 visual analogue scales measuring shame, guilt, self-criticism, self-compassion, normalising and motivation. After phase A, participants will undergo phase B, which is a 4-week intervention period where participants go through 1 module of the guided-self-help materials each week and complete the same visual analogue scales from baseline every day. After phase B, participants will be invited for a follow-up appointment one month after the intervention to fill in the FSDS, FSFI, client satisfaction questionnaire (Larsen et al., 1979) and feedback form developed with experts by experience.

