how often have you been bothered by thoughts that you would be better off dead or of hurting yourself in some way?" - Not at all, Several days, More than half of the days, Nearly every day and a question about support from family and friends. Those who rate themselves as experiencing thoughts of death or self-harm and do not indicate that they have social support or psychological support will not be eligible to participate (see section. Those ineligible to participate will be redirected to a debrief page, 'debrief page for Qualtrics', which will include an explanation of why this is the case and signposting to relevant resources. They will also be provided with the chief investigators email or given the option to leave their telephone number for the chief investigator to call them and discuss why they were not appropriate for the study. Eligible participants will provide informed consent by reading statements relating to the study information and writing their initials if they consent to each statement. This includes confirming they have read the information, understanding participation is voluntary and being able to withdraw from the research at any time. Participants are asked to provide their GP details as part of informed consent. Participants will be informed that their GP will not be notified about their involvement in the study or provided any information contributed whilst participating. We will only contact their GP if there are identified risks. These risks include increased self-harm behaviour, increased suicidal risk or significant deterioration of mental health. Under these circumstances, confidentiality may be breached and, the chief investigator may contact the participants GP. As there is little to no professional contact as part of the study design, the chief investigator will only be made aware of increased risk if the participant raises it to the chief investigator by email.

Eligible participants who provide informed consent will have a screening call with the lead investigator, [name] to verify risk, confirm consent and answer any additional questions about the study. As the intervention is online, we hope that having a call at the

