### **2.3 Material provided to participants.**

#### *2.3.1 Intervention*

[figure not shown]
4 Sessions of guided self-help will be shared with the participants. These will be in the form of handout and video recordings that participant access through Qualtrics. The intervention is based on research on sexual trauma, psychosexual difficulties and materials developed by Bart's NHS Foundation Trust Sexual Wellbeing Service. It has been made in collaboration with clinicians within the service, experts by experience and the chief investigator. The intervention handout and scripts is in the document titled 'Intervention Manual V1'. Within the document there are scripts for each session which are read out in the video recordings. The handouts depict the visual images for the video and the materials provided to participant. Additional handouts for each session can be found in the appendix.

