## 5. Data security, management and confidentiality

### **5.1 Data storage, handling and confidentiality**

All computerised data will be stored and encrypted on a password protected USB drive that adheres to the NHS confidentiality standards.

Participants will provide email address so that they can be sent links to the self-help materials each week as well as links to questionnaire and prompt emails. Names are only used when giving consent and for demographic information. Participants will then be allocated a participation ID number for reference to fill in questionnaires and not linked to names. A separate key associating the ID number with the participants' names will be stored apart from

the data and destroyed once it is no longer necessary to contact participants or obtain further information about them (e.g., once a journal article is published), this file will be password protected.

All information will be submitted through Qualtrics which is a secure and confidential platform. Data will be downloaded, password protected and kept on a secure USB stick, only accessible to the researcher.

Database containing any personal information will be deleted following the final write-up of the research.

No members of the research team will have access to participants' personal medical records or any clinical data beyond that voluntarily provided by the participants when they choose to participate in the study. This information provided will only be seen by the chief investigator and will be kept securely in a password protected database, separately to the research data.

Data will be analysed on a personal laptop by the Chief Investigator at Royal Holloway, University of London. All data will be saved on a password protected encrypted USB (approved by RHUL and sponsor) that only the chief investigator has access to. This will not include any personally identifiable data. Data is anonymised and each participant is given a 4-digit participant code using random numbers and letters.

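### Section 3.3 specifies no reader, decision criteria or masking for the visual analysis of the daily scales, and the only named analyst co-developed the intervention

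*Combined protocol and SAP*

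**What the plan says.** Section 3.3 of the combined protocol and SAP plans the following: "Visual analysis will be performed for daily VAS ratings to evaluate the reliability of treatment effects between the baseline and treatment phases". It does not say who reads the graphs, how many readers there are, what pattern counts as an effect, or what the reader may know. It refers in general terms to What Works Clearinghouse procedures. It also plans two calculated analyses: Tau-U for non-overlap and a reliable change index for pre-post change.

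Section 5.1 supplies the analyst: "Data will be analysed on a personal laptop by the Chief Investigator at Royal Holloway, University of London". The saved data are on an encrypted drive "that only the chief investigator has access to". On the making of the materials, Section 2.3.1 states: "It has been made in collaboration with clinicians within the service, experts by experience and the chief investigator".

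Section 2.1 sets the two phases. On the baseline: "Participants will undergo a baseline period known as phase A, varying between 5- 14 days", and "The number of days participants will be in baseline will be randomly allocated by a randomiser". Phase B follows, "which is a 4-week intervention period where participants go through 1 module of the guided-self-help materials each week".

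**The concern.** Participants know when they start the materials, so their ratings cannot be blinded. The reading of the graphs is a later step at which some masking is feasible. Where a panel shows a plain shift, it matters little who reads it. Where it is ambiguous, the call rests on judgement. A reader who helped make the intervention, and who sees which scale is plotted, knows which call would be favourable. The participant codes in Section 5.1 protect confidentiality but do not hide the scale or its favourable direction.

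At stake is the phase A to phase B comparison of daily ratings, the part of the study to which the randomised baseline length lends experimental control. If ambiguous panels are called in the hoped-for direction, the visual evidence will look more favourable than it is, and the plan contains nothing by which a reader of the report could tell.

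**Working it through.** The plan states no figure for this analysis, so there is nothing to reproduce. The check compares the sections and then tests what masking can achieve.

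**1. Who judges, and by what rule.** Section 3.3 gives no reader, criteria or masking. Section 5.1 gives one analyst with sole access to the saved data. Section 2.3.1 places that analyst among the developers. Neither document mentions masking anywhere.

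**2. Number of judgements.** There are six daily scales (Section 2.1), with a minimum of 6 participants and a target of 20 (Section 2.2).
- Minimum: 6 × 6 = 36 panels.
- Target: 6 × 20 = 120 panels. This is an upper bound, because 20 was chosen to allow for attrition.

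**3. Size of the bias.** If a proportion *f* of panels is wrongly called an effect, the expected count at the minimum sample is 36*f*. The documents give no value for *f*. An assumed range of 5% to 30% gives 36 × 0.05 = 1.8 to 36 × 0.30 = 10.8 panels. That range merely restates the assumption and is not evidence of the bias.

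**4. What hiding the label achieves.** From the items in Section 2.3.2, benefit means a fall on three scales (shame, guilt, self-criticism) and a rise on three (compassion, normalising, motivation). At the minimum sample that is 3 × 6 = 18 panels in each direction. A reader who sees the phase line but not the scale does not know which direction is favourable. Over-calling then no longer runs systematically towards benefit. It also yields unfavourable calls, which show up once labels are restored.

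**5. What the phase line still reveals.** There are 14 − 5 + 1 = 10 possible baseline lengths, and a participant's six panels share one length. Assume lengths are drawn independently and uniformly, since the plan does not say how. The chance that a given participant's length is shared by no one else is then:
- with 6 participants, 0.9^5 = 0.59, so 6 × 0.59 ≈ 3.5 participants have a unique length;
- with 20 participants, 0.9^19 = 0.135, so 20 × 0.135 ≈ 2.7.

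A reader could group those participants' panels by eye and, knowing the baseline lengths, could identify them. Typical score levels may also hint at the scale. The masking is therefore partial.

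**6. Whether panels must also be shortened.** A full series runs 5 + 28 = 33 to 14 + 28 = 42 days, so its length alone gives away the phase change. That would matter if the phase were to be hidden. The aim here is to hide the scale and its favourable direction with the phase line in view, so no phase B days need be dropped.

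**The case against.** The strongest reply has five parts.

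- **Silence is not a plan to read unmasked.** A reader might infer that the graphs will be read with no blind of any kind. The documents do not say so, and the Clearinghouse procedures they cite cannot be checked here. This stands: what can be said is that no masking, reader or criteria are specified.
- **Calculated analyses accompany the reading.** Tau-U does not depend on judging a graph, and this limits the consequence. It does not close the gap: Section 3.3 applies Tau-U to unspecified outcomes and gives no rule for when it disagrees with the visual reading. The reliable change index concerns pre-post scores and does not check the phase A to phase B reading.
- **The daily scales are mostly process measures.** Section 1.3 defines effectiveness by sexual distress and by satisfaction, the latter through confidence and motivation. Of the six scales only motivation appears there. Effectiveness is a secondary objective in the Synopsis and Section 1.3, although primary objective (a) also mentions an initial indicator of it. This largely stands.
- **The analyst may know little about outcomes.** A reader might infer that the chief investigator knows how each participant fared. Section 2.2 says: "Eligible participants who provide informed consent will have a screening call with the lead investigator". That call precedes baseline, and whether the lead and chief investigators are one person is itself an inference. Section 2.2 also describes minimal professional contact, with increased risk becoming known only if a participant emails. This stands. The concern needs only the analyst's part in developing the materials and a visible scale name.
- **The same person would be masking their own data.** This is a fair point. It is eased if the panels are produced before any labelled series is viewed, or if the supervisor who, under Section 5.2, retains the research database runs the script.

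**Conclusion.** The point holds as a gap in specification. An open-ended judgement on 36 panels at the minimum sample is left to a co-developer of the intervention, with no criteria or masking stated, so ambiguous panels may be read towards benefit. The change is worth making because it is cheap and reduces bias.

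A reader might go further and conclude that the study's indicator of effectiveness is inflated. The documents do not support that. They give no rate of ambiguous or wrongly called panels, the main effectiveness measures are self-completed questionnaires, and Tau-U stands beside the visual reading. Nor would masking the reader touch any bias in participants' own ratings.

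The statement that masking would be partial does not depend on a calculation. The figure of about 3.5 identifiable participants out of 6 rests on independent, uniform allocation of baseline lengths and on a reader who knows those lengths.

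**What to change.** In Section 3.3, name the reader and state the following:

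1. The criteria for level, trend and direction of change are written before the data are seen.
2. Before any labelled series is viewed, a script removes participant ID and scale name from each panel, keeps the phase line, and shuffles all panels across participants and scales. Preferably the supervisor identified in Section 5.2 runs it.
3. The reader records level, trend and direction (up, down or none) for every panel and locks the sheet.
4. Labels are then restored and the usual reading across participants follows. Any changed call is reported next to the locked call and the Tau-U result.
5. The report says that the masking is partial and names baseline length and score level as remaining clues.

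The cost is small but not zero: a short script, one extra reading pass made without context, and a small wording change to the access statement in Section 5.1 if the supervisor runs the script. The same reader can do the scoring, so no extra assessor is required, although an independent one would be stronger.

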*Warmth:* Now try to focus of the feelings of warmth and genuine wish to help in the letter as you write it. Spend time breathing gently and really try, as best you can, to let feelings of warmth be there for you. When you have written your letter, read it through slowly, with as much warmth as you can muster. If you were writing to somebody else would you feel your letter is kin.

Remember that this is an exercise that might seem difficult to do at times but with practice you are exercising a part of your mind that can be developed to be helpful to you. Some people find that they can rework their letters the next day so they can think through things in a different way. The key of this exercise is the desire and effort of becoming inwardly gentle, compassionate and self-supportive. The benefits of this work may not be immediate but like 'exercising to get fit' can emerge over time with continued practice. Sometimes people find that even though they are depressed they would very much like to develop a sense of self that can be wise and compassionate to both themselves and others. You can practice thinking about how, each day, you can become more and more as you wish to be. As in all things there will be good times and not so good. Spend time imagining your postures and facial expressions, thoughts and feelings that go with being compassionate and practice creating these inside you.

This means being open with our difficulties and distress, rather than just trying to get rid of them.

Exercise by Paul Gilbert (2007)

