## Study Synopsis

Full Title	Online guided self-help intervention for sexual distress following sexual assault: A single case experimental study
Short Title	Guided self-help following sexual assault - SCED
Protocol version number and date	V2 250722
Study duration	10 months
Study design	Single Case Experimental Design
Sponsor	Royal Holloway, University of London
Chief Investigator	[name]
IRAS Project ID	313482
Primary objective	To test the acceptability and feasibility of an online guided self-help intervention by female survivors of sexual assault who experience sexual distress
Secondary objective	To gain an initial indicator on the effectiveness of the intervention
Number of subject	6
Main inclusion criteria	Cis-female over the age of 18 with an experience of sexual assault that occurred over 12 months ago
Statistical methodology and analysis	Descriptive statistics, visual analysis, reliable change index.

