#### *Secondary objectives*

The secondary outcomes are whether the study suggest the intervention is effective. Is there an initial indicator that the intervention effective? Effectiveness is measured by reduction in the measure of sexual distress and improvement of sexual satisfaction – specifically confidence and motivation in practicing strategies that will improve their experience of sex.

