#### *2.3.2 Visual Analogue Scales*

Visual analogue scales are to be completed by participants. Visual analogue scales are scales with two ends where participants will be asked to rate how much they agree or disagree with the following statements as seen in figure 1 below:

- **Shame**
  - I feel shame when I experience sexual distress
- **Guilt**
  - I have feelings of guilt when I experience sexual distress
- **Self-criticism**
  - When I experience sexual distress, how often do I blame myself or my body?
- **Compassion**
  - When I experience sexual distress, I try to show myself warmth and comfort through my difficulties
- **Normalising**
  - I understand my difficulties in the context of my experience
- **Motivation**
  - I am motivated to put things in place to improve/ address the difficulties in my sex life

Figure 1: VAS Example

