#### *2.3.3 Female Sexual Distress scale – Revised (FSDS-R; Derogatis et al., 2002)*

The FSDS-R is used to assess distress related to sex in women (Derogatis et al., 2002). This 13-item self-report questionnaire is scored has four points, (0: never; 1: rarely; 2: occasionally; 3: frequently). In multiple studies involving more than 500 women, the FSDS-R has shown

high internal consistency (Dergostis et al., 2008) for women with and without sexual difficulties. A validation study demonstrate that the measure has discriminant and content validity (Dergostis et al., 2008). The FSDS-R is completed upon recruitment and at the 1 month follow up.

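### Baseline length is randomised, but section 3.3 names no formal test that uses it and does not say whether Tau-U is descriptive or inferential

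*Combined protocol and SAP*

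**What the plan says.** All section numbers refer to the combined protocol and SAP unless stated otherwise.

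**Design.** Section 2.1 states: "The number of days participants will be in baseline will be randomly allocated by a randomiser". The range is 5 to 14 days, and section 3 repeats it. Six VAS are rated daily through this baseline (phase A) and a four-week intervention (phase B). Section 2.2 sets a target of 20 participants and a minimum of 6, to allow for attrition.

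**Analysis.** Section 3.3 plans descriptive statistics for demographics, visual analysis of the daily VAS across phases, a reliable change index (RCI) for pre-post change, and this: "Tau-U test will be used on outcomes to analyse non-overlap of intervention scores". It ends with a general commitment to What Works Clearinghouse guidance. No significance level is given, and the only wording about statistical significance belongs to the RCI sentence. The synopsis lists "Descriptive statistics, visual analysis, reliable change index" and omits Tau-U.

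**What counts as effectiveness.** It is a secondary objective. Section 1.3 says "Effectiveness is measured by reduction in the measure of sexual distress and improvement of sexual satisfaction", and narrows satisfaction to confidence and motivation. One VAS fits that text: "I am motivated to put things in place to improve/ address the difficulties in my sex life". Section 1.1, however, also names shame and self-criticism as targets of the intervention, and each has its own VAS.

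**Questionnaires.** Section 2.3.3 says "The FSDS-R is completed upon recruitment and at the 1 month follow up". Section 3 says of the same questionnaires: "These questionnaires are filled in once weekly during phase A and B".

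**The concern.** A randomised start day lets a single-case design separate a treatment effect from change that would have happened anyway. The plan sets up that randomisation but names no formal analysis that draws on it.

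Tau-U compares every phase-A rating with every phase-B rating. Its usual standard error treats the ratings as independent, and one person's daily self-ratings may well not be. Phase A also always precedes phase B, so any drift unrelated to treatment appears as non-overlap. If Tau-U p-values were reported, either mechanism could produce a small one, and a later study might build on it. Section 3.3 also leaves the variant, the pooling and the outcomes open, so these could be chosen after the data are seen.

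The primary aim, feasibility and acceptability, is not touched.

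**Working it through.** The plan states no significance level, power or effect size, so there is no figure to reproduce. The anchor is the nominal 5% under independent ratings without drift.

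**Inputs from the documents:** phase A of nA = 5 to 14 days; phase B of four weeks, so nB = 28 daily ratings if complete; six VAS; 6 to 20 participants.

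**Assumed, because the documents give no value:** two-sided 5%; lag-1 autocorrelation φ from 0 to 0.5; drift from 0 to 0.02 SD per day; ten equally likely baseline lengths, drawn independently.

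**1. Tau-U p-value.** S is the number of A-B pairs in which B is higher minus the number in which B is lower, and z = S / √(nA·nB·(nA+nB+1)/3).
- nA = 5: √(5·28·34/3) = 39.8, so p < 0.05 needs |S| > 1.96·39.8 = 78 of 140 pairs.
- nA = 14: √(14·28·43/3) = 75.0, so it needs |S| > 147 of 392 pairs.

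Series were simulated with no effect as y(t) = φ·y(t−1) + √(1−φ²)·e(t), plus drift, with 6,000 series per baseline length and rates averaged over lengths.

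| False positives per series | φ = 0 | 0.2 | 0.3 | 0.5 |
|---|---|---|---|---|
| No drift | 4.8% | 9.6% | 13.3% | 22.9% |
| No drift, baseline-trend corrected | 4.8% | 9.4% | 13.2% | 22.4% |

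The anchor holds at φ = 0. With drift of 0.02 SD per day the rate is 15 to 30% over the same φ, or 14 to 29% with trend correction. That drift separates the phase midpoints by 0.02·(5+28)/2 = 0.33 SD to 0.02·(14+28)/2 = 0.42 SD. The plan does not say that Tau-U would be pooled. If it were, over 6 participants with φ = 0.3 and drift 0.005 / 0.01 / 0.02, the rate would be 17 / 29 / 61%.

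**2. Randomisation test.** Days 1 to 33 (5 + 28) are scheduled under every allocation. The statistic is the mean over participants of (phase-B mean minus phase-A mean) within those days. Baseline lengths are re-drawn 999 times and p is twice the smaller tail. One participant has 10 possible lengths, so a tail cannot fall below 1/10 and pooling is needed; 6 participants give 10^6 allocations.
- *Size:* 4.4 to 5.6% for φ from 0 to 0.5, drift from 0 to 0.02, and 0 or 20% of ratings missing at random. One further setting gave 6.1% in 3,000 runs and 4.7% when repeated with 12,000.
- *Power at φ = 0.3:*

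| Change | 6 participants | 12 | 20 |
|---|---|---|---|
| Immediate 1 SD | 52% | 84% | 97% |
| Immediate 0.5 SD | 18% | 32% | 50% |
| 1 SD built up over 7 days | 12% | 19% | 28% |

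For a linear four-week build-up, power is about 5 to 7%. With 20% of ratings missing, the 1 SD step has 45% (6 participants) and 93% (20).

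**3. Six VAS.** This concerns the added test, not the present plan. With 6 participants, φ = 0.3 and assumed correlation between VAS of 0 / 0.5 / 0.7, at least one of six tests gives p ≤ 0.05 in 26 / 20 / 16% of null runs. Under independence, 1 − 0.95^6 = 26.5%. Holm brings this to 4.8 / 3.9 / 3.0%. If only one VAS changes, Holm lowers power for the 1 SD step to about 24 / 57 / 86% with 6 / 12 / 20 participants.

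**4. Dropout.** Anyone with no rating after day 14 has no phase-B data under a re-drawn 14-day baseline. Suppose half leave, evenly spread over the first week of phase B. The share of leavers affected is 7/7 for baselines of 5, 6 and 7 days, then 6/7, 5/7, 4/7, 3/7, 2/7, 1/7 and 0 for 8 to 14 days. The mean is 6/10, and half of that is 30% of participants. Skipping undefined re-draws kept size at 4.3 to 5.4%.

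**The case against.** **Section 3.3 may already use the start days.** Visual analysis across phases, under the cited guidance, can compare staggered starts informally. This stands. A reader might infer that the randomisation is ignored altogether; the documents do not support that. They support only that no formal test using it is named.

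**Tau-U may be purely descriptive.** It is introduced as a way to look at non-overlap, which fits an index. This also stands. A reader might infer that the plan runs a 5% test with inflated error. The word test makes a p-value plausible, but the plan states neither a p-value nor a level. If Tau-U is descriptive, the error-rate point falls away and section 3.3 needs only to say so. Drift would still bias the index.

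**The added test suits a gradual intervention poorly.** One module is delivered per week, and the letter-writing appendix in the Protocol document says "The benefits of this work may not be immediate". For a slow linear build-up the test has almost no power beyond its own error rate. This limits what the test can show, so it should be supportive only. It does not make an unprotected Tau-U p-value sound.

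**Motivation is not the only candidate for a main VAS.** Section 1.1 gives shame and self-criticism an equal claim, so the choice belongs to the investigators.

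**Conclusion.** The point holds as a gap in specification with a cheap improvement available. The firm part is read from the text: baseline length is random, no named formal test uses it, and the role, variant and outcomes of Tau-U are open.

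The size is conditional. It rests on an assumed p-value reading, an assumed two-sided 5% level, and assumed autocorrelation and drift. Under those assumptions the per-series error on a daily VAS runs from nominal to roughly four to six times nominal. It is nominal when autocorrelation and drift are both zero. Baseline-trend correction removes little of the excess.

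The consequence is confined to the secondary indication of effectiveness. A reader might extend it to the sexual-distress outcome. The documents do not support that: the error rates concern daily VAS series, and they conflict on whether FSDS-R is collected weekly or only at recruitment and follow-up.

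**What to change.** Amend section 3.3 before data are seen:

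1. Report Tau-U as a descriptive overlap index without p-values. Name its variant and the outcomes it covers, after reconciling sections 2.3.3 and 3 on how often the questionnaires are completed. Add it to the synopsis.
2. Add, as a supportive analysis, the two-sided randomisation test pooled over participants described above. Re-draw baseline lengths from the recorded allocation list with its actual probabilities.
3. Fix a rule for missed days (for example, leave them out of the phase means and report their number by phase). Fix another for participants who leave before phase-B data exist under every possible baseline. Either include those with ratings beyond day 14 and report how many are left out, or skip undefined re-draws.
4. Have the investigators name one main VAS and label the other five exploratory, or apply Holm across the six.
5. State that the test has useful power only for a large, prompt change, that a non-significant result is not evidence of no effect, and that the test does not cover FSDS-R.

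**Cost.** SAP wording and analysis code only; nothing changes for participants. There is no p-value per participant. With a 14-day baseline, 33 − 14 = 19 phase-B days are used and 9 of 28 are not. The rules in item 3 assume that missing ratings and leaving do not depend on phase, and the report should say so.
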